Official Title:

Compensatory Kinematic Movements in Various Directions After Stroke

NCT Number:

NCT05683158

Document Date:

July 19, 2022

Statistical Analysis

Statistical analyses were performed using various methods to comprehensively evaluate the data. For comparing demographic and clinical characteristics between the two groups, both chi-square test and t-test were employed.

The main analysis utilized two-way mixed-design analyses of variance, conducted independently for each variable. This analysis incorporated three levels as the within-subject factor and the participant group (healthy, stroke) as the between-subject factor. To account for multiple comparisons, Bonferroni post-hoc tests were performed. All statistical analyses were conducted using a significance level (α) of $p < 0.05$.

Sample size determination was carried out using G*Power V.3.1 software (Franz Paul, Kiel, Germany) (Faul et al., 2007). The calculation parameters included an effect size (d) of 1.9, significance level (α) ≤ 0.05 , power = 0.8, and type II error (β) = 0.2, following the methodology of previous research (Machado et al., 2019).

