NCT number: NCT05683158

Research protocol (Human subject study)

Research project title

[figure not shown]
Compensatory kinematic analysis in various directions after chronic stroke

Methodology and Design

The inclusion criteria for the participants with stroke were physician-confirmed chronic hemiplegia (≥ 6 months onset), Mini-Mental State Examination ≥ 25 , Modified Ashworth Scale (MAS) (biceps ≤ 2 , triceps ≤ 2), ability to sit alone on a chair, and FMA upper extremities score ≥ 21 . The healthy participants were individuals without any history of neurological or orthopedic diseases.

[figure not shown]
- The exclusion criteria were muscle flaccidity, neglect syndrome, orthopaedic diseases, and poor coordination.

* The specific placement of markers

- Sternum, xyphoid process, Both acromion, C7, T4, elbow(lateral and medial epicondyle), wrist (lateral and medial styloid process), finger 3rd MCP

The seated reaching task posture is as follows:

- The participant attempts to reach the target using the affected upper limb
- The seated height is adjusted to 100% of the participant's lower limb length, with the feet flat on the floor and the knees bent at a 90 degree angle. A chair with adjustable height is used to achieve this.
- Reaching movements are categorized into three directions: forward, ipsilateral and contralateral direction.
- The task is performed five times in a comfortable speed for each direction, and for analysis purposes, three out of the five trials are selected to calculate the average time.

1. Clinical assessment

1-1. Fugl-Meyer motor Assessment of the Lower Extremity (FMA-UE) Assessment of sensorimotor function:

A. UPPER EXTREMITY, sitting position				
I. Reflex activity				
Flexors: biceps and finger flexors (at least one)	0	2		
Extensors: triceps	0	2		
Subtotal I (max 4)				
II. Volitional movement within synergies, without gravitational help				
Flexor synergy: Hand from contralateral knee to ipsilateral ear. From extensor synergy (shoulder adduction/ internal rotation, elbow extension, forearm pronation) to flexor synergy (shoulder abduction/ external rotation, elbow flexion, forearm supination).	Shoulder Elbow Forearm	retraction elevation abduction (90°) external rotation flexion supination		
Extensor synergy: Hand from ipsilateral ear to the contralateral knee	Shoulder Elbow Forearm	adduction/internal rotation extension pronation		
Subtotal II (max 18)				

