- (0) Cannot stand on nonparetic leg

5. Standing on Paretic Leg

Examiner: Have the subject stand on the paretic leg. Evaluate only the ability to bear weight entirely on the paretic leg. Do not consider how the subject accomplishes the task.

- (3) Can stand on paretic leg for more than 10 seconds
- (2) Can stand on paretic leg for more than 5 seconds
- (1) Can stand on paretic leg for a few seconds
- (0) Cannot stand on paretic leg

Maintaining Posture SUBTOTAL _____

Safety evaluation criteria and evaluation methods

Before starting the experiments, the health and physical condition of the subjects are assessed, and within 24 hours after the experiment, and signs of physical abnormalities are monitored.

Data analysis and statistical methods

To determine the sample size, the G * Power V.3.1 was utilized (Franz Paul, Kiel, Germany) (Faul F et al., 2007) incorporating an effect size of 0.44, $\alpha < 0.05$, power = 0.80, requiring total sample size of 12 participants (Dos Santos et al., 2019).

1. Statistical analysis was performed with IBM SPSS (version 28.0.1.1 (14)). Data were tested for normality using the Kolmogorov-Smirnov test. Kinematic data did not significantly deviate from a normal distribution ($P > 0.05$). The Chi-square test was used to assess the sex distribution of the participants. The independent *t*-test and Mann-Whitney *U* test, as a nonparametric test, were employed to compare the two groups concerning specific demographic and clinical characteristics.

In the event of an unforeseen emergency, the participant's condition will be assessed, and immediate contact

Predicted side effects and precautions with corresponding measures

will be made with emergency medical personnel for necessary actions. Subsequently, a prompt report will be submitted to the Institutional Review Board (IRB)

Criteria for discontinuation and dropout

1. Inability to independently perform the action of sitting and extending the paralyzed arm
2. Feeling of dizziness

Risks and benefits to research participants

- Prior to the start of the experiment, participants will receive a comprehensive explanation of the entire experimental procedure and the potential risks involved through an informed consent document. They will proceed with the experiment after understanding and acknowledging these risks.

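### Does the SAP's silence on sphericity leave the direction tests with inflated type I error?

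*SAP*

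**What the plan says.** The SAP, under Statistical Analysis, specifies "two-way mixed-design analyses of variance, conducted independently for each variable". The between-subject side is "the participant group (healthy, stroke) as the between-subject factor". For the repeated side it says only "This analysis incorporated three levels as the within-subject factor", without naming the levels. The Protocol, under Methodology and Design, supplies the natural reading: "Reaching movements are categorized into three directions: forward, ipsilateral and contralateral direction".

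The only assumption check in either document is in the Protocol's section on data analysis and statistical methods: "Data were tested for normality using the Kolmogorov-Smirnov test". The same section names SPSS as the software and gives the size of the study, "requiring total sample size of 12 participants", without a split by group. The SAP adds Bonferroni post-hoc tests and a 5% significance level. Neither document mentions sphericity, Mauchly's test, an epsilon correction, a multivariate test or a covariance structure.

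**The concern.** A repeated factor with three levels has two numerator degrees of freedom. The standard F tests for that factor and for its interaction with group hold their size only if all pairwise differences between levels have the same variance (sphericity). Reaching forward, to the same side and across the body are different movements, so equal variances cannot be taken for granted. A normality test says nothing about this, and Bonferroni adjustment of post-hoc comparisons does not repair the omnibus F tests.

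The two affected tests are the ones that answer the question in the study's title, and the gap recurs in the ANOVA for every variable. If the uncorrected results were used and sphericity failed, direction effects would be declared too often. A reader could not tell from the SAP which p-value decides.

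**Working it through.** **Inputs.** From the documents: 2 groups and 3 within-subject levels (SAP); total N = 12, effect size 0.44, power 0.80 (Protocol); alpha 0.05 (both). Assumed because the documents do not say: a 6+6 split, normal data, the same covariance matrix in both groups, and, for the sample size only, a within-subject correlation of 0.5.

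**The Protocol's own figure.** Read 0.44 as Cohen's f for the group-by-direction interaction. With correlation 0.5 and epsilon 1, the noncentrality is f² × N × 3 / (1 − 0.5) = 0.1936 × 12 × 3 / 0.5 = 13.9. On 2 and 20 degrees of freedom this gives power 0.88, and 12 is the smallest even N that reaches 0.80. So 12 can be reproduced, and it fixes the error degrees of freedom at (12 − 2) × 2 = 20.

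**Worst case, exact.** Let λ₁ and λ₂ be the eigenvalues of the covariance of the two orthonormal direction contrasts. Then epsilon = (λ₁ + λ₂)² / [2(λ₁² + λ₂²)], which runs from 0.5 to 1. The uncorrected critical value is F(0.95; 2, 20) = 3.493. At epsilon 0.5 one eigenvalue is zero and the statistic follows F(1, 10), so the true size is P(F(1, 10) > 3.493) = 0.0912.

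**Between the extremes.** Simulated rejection rates for the interaction under a true null, 200,000 data sets per row, 6+6. The direction effect behaves the same way.

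| Epsilon | Uncorrected F | Greenhouse-Geisser always | Greenhouse-Geisser only if Mauchly's p < 0.05 | Mauchly's test significant |
|---|---|---|---|---|
| 1.0 | 5.0% | 4.1% | 4.9% | 5% |
| 0.9 | 5.5% | 4.4% | 5.3% | 13% |
| 0.75 | 6.5% | 4.8% | 5.7% | 37% |
| 0.6 | 7.9% | 5.1% | 5.5% | 86% |
| 0.5 | 9.0% | 5.0% | 5.0% | 100% |

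The last uncorrected entry differs from the exact 9.1% only by simulation error. The group main effect uses each participant's mean over directions, has one degree of freedom and stays at 4.9% to 5.1%.

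**What a firm rule would buy.** Mauchly's test misses moderate departures at this size, but those are the departures that do little damage. Where the damage is large, the test usually finds it. The conditional procedure therefore peaks at 5.7%. Correcting always gives 4.8% at that point, a gain of 5.7 − 4.8 = 0.9 percentage points.

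**What it would cost.** Take an effect for which the uncorrected test has 80% power under sphericity. Greenhouse-Geisser applied always has about 77%. Applied only after a significant Mauchly's test, it has about 79.5%.

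**What it would not cover.** All these rates need equal covariance in the two groups. Suppose, as an assumption only, that stroke variances are four times healthy ones and the split is 4 stroke and 8 healthy. Under sphericity the uncorrected F then rejects in about 15% of samples and Greenhouse-Geisser still in about 13%. At 6+6 with the same variances the rates are 5.7% and 4.6%.

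**The case for a change.** The strongest case for a change is that it is cheap. One sentence naming the correction settles which p-value decides, needs no new data and removes any choice made after seeing results. The inflation also hardly depends on the sample size: at epsilon 0.5 it is still 8.7% with 24 participants and 8.6% with 40. And nothing in the documents justifies assuming epsilon equal to 1.

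Much of this stands. The omission is real, the arithmetic is right, and a sentence on sphericity would make the SAP tidier.

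It does not show a fault in the plan, because the harm depends on two unknowns together: that the uncorrected result is the one read, and that epsilon is well below 1. The SAP says neither. It is a three-paragraph summary written in the past tense, so a correction may already have been used. Nor is there one right correction to insist on: Greenhouse-Geisser, Huynh-Feldt or a multivariate test would all serve. Post-hoc comparisons of two directions, each with its own error term, do not need sphericity at all.

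**Conclusion.** No change follows. The SAP leaves unsaid whether its within-subject F tests are corrected, which is a gap in detail that analysts fill by routine. If no correction were made, type I error for direction and for group by direction would lie between 5.0% and 9.1%, with the upper end reached only at the theoretical floor of epsilon. With the usual check and correction it lies between 4.9% and 5.7%. A mandatory correction would gain at most about one percentage point over that practice and would give up about three points of power relative to the uncorrected test under sphericity, in a study of 12.

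These figures rest on N = 12, normal data, a 6+6 split and a common covariance in the two groups. The last assumption matters most: with unequal covariances and unequal group sizes the rates can go well outside this range, and an epsilon correction would not prevent it. The conclusion would differ if the SAP had prescribed the uncorrected test, or if the documents gave an epsilon well below 1.

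### The SAP's single-step Bonferroni post-hoc tests are valid, but Holm's step-down gives the same 5% family-wise control with equal or greater power; the gain depends on a family and an effect size that the documents leave open

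*SAP*

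**What the plan says.** The SAP fits a two-way mixed analysis of variance separately for each variable: "This analysis incorporated three levels as the within-subject factor and the participant group (healthy, stroke) as the between-subject factor". On multiplicity it has one sentence: "To account for multiple comparisons, Bonferroni post-hoc tests were performed". The level is 0.05 throughout. The SAP does not say which comparisons form a family. Neither document mentions a step-down procedure or simultaneous confidence intervals.

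The protocol's description of the seated reaching task gives the three levels: "Reaching movements are categorized into three directions: forward, ipsilateral and contralateral direction".

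The sample-size inputs differ between the documents. The SAP says "The calculation parameters included an effect size (d) of 1.9", with "power = 0.8, and type II error (β) = 0.2", and gives no number of participants. The protocol's section on data analysis and statistical methods says "incorporating an effect size of 0.44", without naming the metric, and ends with "requiring total sample size of 12 participants". Neither document states how the 12 divide between stroke and healthy participants.

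**The concern.** Single-step Bonferroni holds every comparison in a family of three to 0.05/3 = 0.0167, whatever the other two show. Holm holds only the smallest p-value to that threshold, then moves to 0.05/2 and 0.05 as hypotheses are rejected. Both control the same error rate, so Bonferroni gives up power without any gain in protection.

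The study asks how compensatory movement differs by direction, and the post-hoc tests are where the directions are told apart. With 12 participants, an avoidable loss of power there deserves attention.

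**Working it through.** **Inputs.** From the SAP: d = 1.9, alpha 0.05, power 0.80, Bonferroni. From the protocol: total 12, three directions, effect size 0.44. Assumed because not stated: 6 per group, two-sided tests, normal data with equal variances, correlation between directions 0 to 0.9, and (steps 2 to 6) a family of three stroke-versus-healthy tests, one per direction.

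**1. Reproducing the total of 12.** For a two-sample t-test with n per group, power is P(|T| > t_crit), where T is noncentral t with 2n - 2 degrees of freedom and noncentrality d × √(n/2).
- n = 5: 1.9 × √2.5 = 3.00; power 74.9%.
- n = 6: 1.9 × √3 = 3.29; power 84.2%.

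So d = 1.9 leads to 12. The protocol's 0.44 can lead there too: read as Cohen's f in a 2-group, 3-measure repeated-measures ANOVA (within or interaction term, assumed correlation 0.5), it gives 79.7% at N = 10 and 88.2% at N = 12. The total therefore does not show which effect size was used.

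**2. Bonferroni.** The same formula with n = 6 and alpha = 0.05/3 gives **66.3%** per direction.

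**3. Holm, d = 1.9 in all three directions.** Ordered p-values are compared with 0.05/3, 0.05/2 and 0.05, stopping at the first failure (100,000 simulated trials per scenario).

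| Correlation | Holm, per direction | Gain over 66.3% | All three found: Bonferroni | All three found: Holm |
|---|---|---|---|---|
| 0 | 78.6% | 12 points | 29% | 57% |
| 0.3 | 77.6% | 11 points | 36% | 61% |
| 0.5 | 76.5% | 10 points | 40% | 64% |
| 0.7 | 75.6% | 9 points | 46% | 67% |
| 0.9 | 73.7% | 7 points | 55% | 71% |

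**4. Other patterns of effect, same family.**
- All present but unequal (2.5, 1.9, 1.3): average gain 9 to 10 points.
- Two directions at 1.9, one at 0: gain 4 to 5 points in each true direction at correlation 0 to 0.7. At 0.5, for example, 66.2% becomes 70.6%.
- One direction at 1.9, two at 0: gain about 0 (66.1% to 66.2% at correlation 0.5).

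**5. The protocol's 0.44 in all three directions, 6 per group.**
- Read as d: gain 0.2 to 1.2 points (4.3% to 4.8% at correlation 0.5).
- Read as f, so d = 2 × 0.44 = 0.88: gain 1.4 to 3.5 points (14.0% to 16.6% at correlation 0.5, the gain being 2.7 points before rounding).

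**6. Family-wise error.** Holm's simulated error was at most 5.0% in every null or partly null case. With all three null at correlation 0.5 it was 4.57%, the same as Bonferroni. With two true effects at correlation 0.5 it was 3.72%, against 1.64% for Bonferroni.

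**7. The other plausible family: three pairs of directions.** The documents give no effect size for these, so the inputs are illustrative: paired tests in 6 participants, one direction 1.5 SD from the other two, correlation 0.7. Power per true difference goes from 82.5% (Bonferroni) to 87.4% (Holm), about 5 points. Both true differences are found in 71% (Bonferroni), 81% (Holm) and 90% (Shaffer). Shaffer's thresholds 0.05/3, 0.05, 0.05 are valid here because, once one equality among three means is false, at most one of the other two can be true. With one direction only 0.5 SD apart, Holm's gain per true difference is about 1 point (11.4% to 12.4%).

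**The case against.** The strongest reply is that Bonferroni is valid and conservative, that the plan protects its error rate, and that no size can be put on the loss. Much of this stands.

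- **The family is undefined.** Only the direction factor has more than two levels, so pairs of directions are at least as natural a reading as three group comparisons. This changes the size of the gain but not its sign.
- **The effect size is contested.** The 1.9 and the 12 never appear together; the 12 stands beside 0.44. Under 0.44 the gain is small.
- **A reader might infer that about 10 points of power per direction are lost for nothing.** The documents do not support that as a general statement. It needs d = 1.9 in all three directions, which neither document states. Bonferroni also has one real advantage, simple matching simultaneous intervals, although the SAP plans none.
- **A reader might infer that the adjustment decides how many directions are declared different.** Usually it does not. The two methods give identical decisions in 68-77% of simulated trials in the best case, about 88-90% with two true effects, and 98-99% with one (correlation 0 to 0.7).
- **Timing matters.** Both documents describe analyses in the past tense, and the protocol already reports a normality result for the kinematic data. Moving to a more liberal rule after seeing the comparisons would be a post hoc change in favour of significance.

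What survives is that Holm never rejects less at the same family-wise error, whatever the family, effect size, allocation or correlation.

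**Conclusion.** The point holds as a conditional, inexpensive improvement. The superiority of Holm over single-step Bonferroni is a logical result and needs no assumption about this trial. The size does need assumptions. In the best case (three stroke-versus-healthy tests, 6 per group, d = 1.9 throughout, correlation 0 to 0.7) power per direction rises from 66% to about 76-79%. It rises by 4-5 points if two directions differ, by about 0 if one does, and by about 0-3 points under 0.44.

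Even in the best case Holm does not bring power per direction to 80% with 12 participants. Nor should one conclude that the SAP's 80% ought to be replaced by 66%. The SAP does not claim 80% for adjusted comparisons, and 66% rests on an assumed family, an assumed equal split and an effect size on which the two documents disagree.

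**What to change.** In the SAP, replace the Bonferroni post-hoc tests with Holm step-down adjusted post-hoc tests within each family of three (ordered p-values against 0.05/3, 0.05/2 and 0.05), and report Holm-adjusted p-values. The same sentence should say which three comparisons make up a family. Shaffer's thresholds are optional if the family is the three pairs of directions.

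Make the change before the comparisons are examined. If they have already been examined, disclose the change as post hoc and report the Bonferroni results alongside. Do not write 66% into the SAP as the study's power; reconcile 0.44 with 1.9 before giving any power for these comparisons.

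The cost is one sentence and the sorting of three p-values, with no extra participants or measurements. The small downside is that simultaneous confidence intervals matching Holm are less simple, so keep Bonferroni or unadjusted intervals for estimation.
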